During the screening period, patients will be entered into the study on the basis of inclusion and exclusion criteria. Patients will have the option to provide a blood sample for biomarker research within 3 hours prior to the first dose (preferably at the same time as the first pre-study drug infusion cytokine blood sample) and a blood sample for genotyping. Patients (or their legally authorised representative) who agree to take part in the genetic research will be asked to sign a separate informed consent form to confirm their willingness to have this sample taken. Patients (or their legally authorised representative) who agree to take part in the biomarker research will be asked to sign either a separate informed consent form or note consent in a specific section of the general informed consent form to confirm their willingness to have this sample taken. The samples will be stored and may be analysed in future research.

Eligible patients (ie, those who have met the study inclusion and exclusion criteria) will be randomised in a 1:1:1 ratio to receive either AZD9773 250/50 units/kg or AZD9773 500/100 units/kg or placebo (saline). Dosing will be determined by body weight (taken at screening as close as possible to the first dose but within 24 hours before the first dose) up to 100 kg. Patients with a body weight >100 kg will receive doses corresponding to 100 kg.

Treatment period (Day 1 up to Day 5)

Day 1 begins at the start of the first dose (within 24 hours of qualifying organ failure) and continues until the end of that calendar day.

AZD9773 250/50 units/kg (Dose arm 1):

Single iv loading infusion of 250 units AZD9773 per kg body weight (maximum 25000 units) in a volume of 250 mL over 30 minutes followed by 50 units AZD9773 per kg body weight in a volume of 100 mL over 30 minutes once every 12 ± 2 hours for up to a maximum of 9 iv maintenance doses (maximum 5000 units each) or until the patient no longer requires haemodynamic or ventilatory support and ICU care and there is no evidence of worsening organ failure (see below for duration of treatment).

AZD9773 500/100 units/kg (Dose arm 2):

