6.2.1 Procedures for randomisation

Patients will be randomised to treatment following verification of conformance with eligibility criteria at screening. Central randomisation via IVRS will be used to allocate patients to treatment groups (AZD9773: dose 1, dose 2, placebo) in a 1:1:1 ratio and avoid selection bias.

Randomisation will be performed in blocks based on a computer-generated randomisation scheme provided by AstraZeneca. The size of randomisation blocks will not be disclosed to the study centres. Randomisation will not be stratified. The randomisation scheme will randomly assign the study drug to the randomisation numbers.

Randomisation codes will be assigned strictly sequentially as patients become eligible for randomisation. Randomised patients who terminate their study participation for any reason, regardless of whether the study drug was taken or not, will retain their randomisation number. The next patient will be given the next randomisation number.

Patients who are withdrawn after randomisation will not be replaced.

Sections [6.3.1](#) and [6.3.2](#) describes procedures for blinding and breaking the blind.

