13. STATISTICAL METHODS AND SAMPLE SIZE DETERMINATION BY ASTRAZENECA

13.1 General principles

A comprehensive SAP will be finalised before the last patient visit. All statistical analyses will be performed by PAREXEL. Any deviations from those analyses presented here and/or in the SAP will be detailed in the clinical study report. All outputs will be produced using SAS[®] version 9 or later in accordance with AstraZeneca standards.

All study data will be analysed after the 28-day follow up is complete for all patients. A further analysis will be performed using the Day 90 assessment to understand longer-term patient outcomes (survival and HRQoL).

The following efficacy endpoints will be subject to formal statistical analysis: VFDs, 7-day mortality, 28-day mortality, mortality at Day 90, organ failure-free days, shock-free days and ICU-free days. All other data will only be summarised.

All efficacy data will be summarised and analysed using the per protocol (PP) population. Additionally, an ITT analysis of the endpoints listed above for formal analysis will also be undertaken using the ITT population.

For each of the endpoints subject to statistical analysis the following statistical comparisons will be performed: AZD9773 dose 1 versus placebo, AZD9773 dose 2 versus placebo, and combined AZD9773 dose arms 1 and 2 versus placebo. Although there are three primary comparisons, this is an exploratory Phase IIb study and consequently no adjustment for multiple comparisons will be made.

Unless stated below, no imputation of missing data will be performed. All data recorded on the database will be included in data listings. Any spurious or erroneous data will be queried and followed up until satisfactorily resolved.

The nominal significance level used for this study will be 10% one-sided. However, it is important to note that the study has only been sized based on VFDs over 28 days; this study is not powered to detect a statistically significant difference in 7-day mortality, 28-day mortality or mortality at Day 90. In this case the confidence intervals (CIs) will provide a guide to the possible range of the true treatment effect. This may also be the case for the other secondary endpoints.

Demography data will be summarised using the PP and ITT populations and safety data will be summarised using the safety population. For all summaries of change from baseline, baseline is defined as the latest non-missing assessment prior to first study drug infusion.

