13.3.4 Ventilator-free days

Summary statistics (mean, median, standard deviation [SD], minimum, and maximum) of VFDs over 28 days will be presented by treatment group. Missing data will be handled using a last observation carried forward (LOCF) approach when calculating VFDs for each patient. A histogram of VFD will also be produced for each treatment group.

For the formal statistical analysis, an analysis of covariance model will be fitted for VFDs allowing for treatment group and the following baseline covariates:

APACHE II score (four categories based on the quartiles of the baseline score), age (two categories: <60 and 60 or older), region (three categories: Australia, North America [Canada & USA] and All Other) and an indicator variable if the patient was on mechanical ventilation at baseline (two categories: yes or no).

The difference in VFDs for each of the comparisons: AZD9773 dose 1 versus placebo, AZD9773 dose 2 versus placebo, AZD9773 dose 1 and 2 versus placebo will be presented in terms of the difference in the Least Square Means (LSMeans) and the associated two-sided 80% CI and one-sided p-value. Additionally, a two-sided 95% CI and two-sided p-value will also be presented.

For the PP population, the effect of other baseline variables (examples include baseline TNF, Xigris use prior to study treatment and presence of shock at baseline) on the treatment comparisons will also be explored via a series of analyses including the covariates as specified above for each of the levels of these baseline variables separately. The difference in the treatment LSMean and the associated two-sided 80% CI from these analyses (along with the results from the baseline covariates fitted in the statistical analysis above) will be presented graphically on the same plot. Additionally, an analysis of variance will also be performed for the PP and ITT populations (with no covariates and only treatment as a factor).

VFDs at Day 15 (over 14 days) will be analysed in a similar manner to above.

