13.3.6 Organ failure-free days, shock-free days, and ICU-free days

Organ failure-free days, shock-free days, and ICU-free days will be summarised and analysed in the same way as for VFD (see Section 13.3.4).

13.3.7 7-day mortality, 28-day mortality and mortality at Day 90

Seven-day mortality and 28-day mortality will be summarised by treatment group. The formal analysis will be undertaken for each the comparisons: AZD9773 dose 1 versus placebo, AZD9773 dose 2 versus placebo, AZD9773 dose 1 and 2 versus placebo separately using a Cochran-Mantel-Haenszel test in which the test will be stratified using the same covariates as for VFD. The corresponding relative risk, two-sided 80% CI and one-sided p-value will be calculated using the procedure PROC FREQ in SAS. Additionally, a two-sided 95% CI and two-sided p-value will also be presented.

An unstratified analysis will also be performed for the PP and ITT populations. Additionally, for the PP population, the impact of other baseline variables (examples include baseline TNF, Xigris use prior to study treatment and presence of shock at baseline) on the treatment comparisons will be explored by undertaking a series of analyses for each of the levels of these baseline variables separately, and the relative risks along with the associated two-sided 80% CIs from these analyses will be presented graphically.

In the event that the 7-day mortality and 28-day mortality status is unknown for some patients, they will be excluded from the PP population. However, for the ITT population they will be included as though they had died. Further sensitivity analyses may be undertaken depending on the number of such patients.

A Kaplan-Meier curve of time to death will also be produced and both a stratified (using the same covariates as for the analysis of 7 and 28-day mortality) and unstratified log rank test will be undertaken. If the 7-day or 28-day mortality status is unknown for some patients, they will be censored at the last known date the patient was alive.

Mortality at Day 90 will be considered in the same way as 7-day and 28-day mortality.

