13.4 Determination of sample size

The sample size has been based on the primary outcome variable of VFDs over 28 days. The Phase IIb study in 81 patients with D-CytoFab has been used as an estimate of the between-patient SD (11.380). Assuming this SD holds for the current study, then 100 patients per group will provide 90% power to detect an underlying true difference in means between a dose of AZD9773 and placebo of 4.2 days using a 10% one-sided significance level.

Given this is an exploratory Phase II study, a 10% one-sided significance level is considered appropriate as this implies a 1 in 10 chance of a false positive finding which is consistent with the aim in Phase II of identifying a promising therapy.

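### The subgroup analyses aim at effect modification, but no stated analysis estimates the difference in treatment effect between levels

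*Protocol*

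**What the plan says.** Protocol section 13.3.4 sets out to explore, in the per-protocol population, how further baseline variables act on the treatment comparisons for ventilator-free days (VFDs). Baseline TNF, Xigris use before study treatment and shock at baseline are named as examples. The method is fixed: it proceeds "via a series of analyses including the covariates as specified above for each of the levels of these baseline variables separately". The LSMean differences and two-sided 80% CIs go on one plot, together with results for the covariates of the main model. The synopsis (Statistical methods) repeats this.

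Section 13.3.6 sends organ failure-free, shock-free and ICU-free days through the same analysis as VFDs. Section 13.3.7 treats the mortality endpoints in parallel, by "undertaking a series of analyses for each of the levels of these baseline variables separately", and plots relative risks with 80% CIs. Unlike 13.3.4, it does not say that the covariates are carried into each level.

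No section states a treatment-by-variable term, an estimate of the difference between levels, a homogeneity test or a minimum level size. The work is described as exploratory and has no decision rule.

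**The concern.** Whether a baseline variable changes the treatment effect is a question about a difference between two effects. The plan produces each effect with its own interval and stops there. A reader who wants the answer has to compare intervals by eye. The most natural comparison, whether one interval excludes zero while the other does not, is a poor guide: two levels with identical true effects will often disagree because each holds only part of the sample.

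A second, conditional problem is that the whole covariate set and the residual variance are re-estimated inside every level. Where a level is small, this costs precision.

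At stake is the interpretation of the exploratory subgroup displays. The primary comparison of each dose with placebo is not touched.

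**Working it through.** **Inputs.** Section 13.4: SD 11.380; "100 patients per group will provide 90% power" for a "difference in means between a dose of AZD9773 and placebo of 4.2 days using a 10% one-sided significance level". Section 13.1: "The nominal significance level used for this study will be 10% one-sided", which corresponds to one limit of a two-sided 80% CI (z = 1.2816). Section 4.1: patients "will be randomised in a 1:1:1 ratio". Section 6.2.1: "Randomisation will not be stratified", so equal arm sizes within a level are an approximation. Level sizes are not given; splits from 50/50 to 10/90 of 100 per arm are assumed. The calculation is for one dose against placebo, unadjusted.

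**The plan's own figure.** SE = 11.38 × √(2/100) = 1.609. Power = Φ(4.2/1.609 − 1.2816) = Φ(1.328) = 0.908, which agrees with the stated 90%.

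**Chance that two levels look different.** The true effect is 4.2 days in both, so there is no interaction. For n per arm in a level, SE = 11.38 × √(2/n) and p = Φ(4.2/SE − 1.2816) is the chance that its 80% CI lies wholly on the drug-favouring side. Discordance = p1(1 − p2) + p2(1 − p1).

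| Split | p, larger level | p, smaller level | Discordance |
|---|---|---|---|
| 50/50 | 0.714 | 0.714 | 0.41 |
| 70/30 | 0.816 | 0.559 | 0.46 |
| 80/20 | 0.854 | 0.454 | 0.53 |
| 90/10 | 0.884 | 0.324 | 0.64 |

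For example, at 90/10: 0.884 × 0.676 + 0.324 × 0.116 = 0.635. If exclusion of zero on either side is counted, the 90/10 figure is 0.62 and the others barely move. With a true effect of zero in both levels, the either-side figure is 2 × 0.2 × 0.8 = 0.32.

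**The quantity the plan leaves out.** The difference between the level estimates has SE √(SE1² + SE2²):
- 50/50: √(2.276² + 2.276²) = 3.22 days, so an 80% CI half-width of 1.2816 × 3.22 = 4.1 days.
- 90/10: √(1.696² + 5.089²) = 5.36 days, half-width 6.9 days.

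With no true interaction, a chance gap larger than 4.2 days occurs in 19% of cases at 50/50 and 43% at 90/10. By construction, an 80% CI for the gap itself would exclude zero in 20% of cases at any split.

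**Power of the interaction.** At 50/50 and two-sided 10%: Φ(4.2/3.22 − 1.645) = 0.37 for a 4.2-day interaction, and Φ(8.4/3.22 − 1.645) = 0.83 for an 8.4-day one.

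**Small levels (ANCOVA endpoints only).** Parameters per fit: intercept 1, treatment 2, APACHE II quartiles 3, age 1, region 2, ventilation 1, total 10. A level with 10 per arm has 30 patients and 30 − 10 = 20 residual df. The design was simulated with assumed covariate frequencies (region 20/60/20, 75% ventilated, other categories equal). The median 80% half-width was 2.1 days at 300 patients in the level, 4.0 at 90, 5.0 at 60 and 8.0 at 30. Without covariates and with the SD taken as known, 10 per arm gives 1.2816 × 5.089 = 6.5 days. About 0.3% of fits at 30 patients could not estimate every term.

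**The case against.** The strongest reply is that the discordance rates measure a misreading. The protocol never says to compare which intervals exclude zero. Per-level estimates on one plot are a recognised exploratory display, and wide intervals announce their own uncertainty. Under another visual reading, whether the two 80% CIs fail to overlap, chance disagreement is only 7% (50/50) to 10.5% (90/10). Much of the rise towards 64% is low power in the smaller level. Level intervals taken from a pooled model would disagree about zero nearly as often. All of this stands. It means that the gain lies in reporting the interaction, and that re-deriving the level estimates would achieve little.

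It can also be said that interaction tests belong in the SAP, which is not shown and could add one. That is possible. But the protocol does more than leave a detail open: it states the aim and fixes a method that does not deliver the quantity the aim concerns.

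Replacing the per-level models outright would be a trade-off. A pooled model assumes a common residual variance and common covariate effects. VFDs are bounded and set to zero for death (section 12.2.6), so variances may differ between, say, shocked and non-shocked patients. This is a good reason to keep the per-level fits.

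A reader might infer that these plots will select the population of the next trial. The documents do not say so: section 4.2 speaks of determining the dose regimen for further studies, and sections 13.3.4 and 13.3.7 speak of exploring.

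**Conclusion.** The point holds as a modest improvement to an exploratory analysis. The stated aim concerns effect modification, and the stated methods in 13.3.4, 13.3.6 and 13.3.7 do not estimate it.

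The 41% to 64% range applies only to a reader who compares intervals against zero. It assumes the design SD and effect, equal arms within levels and the splits shown. It is not a false-positive rate of any test in the plan. Covariate adjustment would narrow the intervals somewhat, and per-protocol exclusions would widen them.

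A reader might also infer that small levels are bound to give unstable fits. The documents give no frequency for prior Xigris use or any other level. Imprecision becomes marked at about 30 patients or fewer across the arms, is negligible at about 90 or more, and whether any level will be that small is unknown. The parameter-count argument does not extend to mortality, because 13.3.7 does not describe a covariate model within levels.

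**What to change.** Keep the exploratory plot and the per-level analyses. In 13.3.4, and through it 13.3.6, add for each baseline variable one model on all per-protocol patients with the planned covariates, the variable and a treatment-by-variable term. Print the interaction estimate with its 80% CI beside the level estimates; a p-value is optional. In 13.3.7, add the ratio of relative risks between levels or a test of homogeneity across them. Make the matching change in the synopsis.

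The cost is a few model terms and an extra column on each plot. The pooled model brings the two assumptions of common residual variance and common covariate effects, which should be stated. With about 37% power for a 4.2-day interaction in an even split, the text should also say that a non-significant interaction is not evidence of a consistent effect. These results would remain unadjusted and exploratory, like the plots they accompany.

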13.3.5 Modified Sequential Organ Failure Assessment (SOFA) Score

Summary statistics (mean, median, SD, minimum, and maximum) of the raw data and change from baseline to each scheduled study assessment for each component and the total modified SOFA Score will be presented by treatment group.

For missing coagulation, liver and renal of the total modified SOFA score, a LOCF approach will be used and the last assessment performed should be the value for that day. For cardiovascular and respiratory components, investigators will be encouraged to use other available data (on/off vasopressors, percentage oxygen saturation in order to complete the individual component score).

The worst BP and saturation values of the day should be used.

13.3.6 Organ failure-free days, shock-free days, and ICU-free days

Organ failure-free days, shock-free days, and ICU-free days will be summarised and analysed in the same way as for VFD (see Section 13.3.4).

13.3.7 7-day mortality, 28-day mortality and mortality at Day 90

Seven-day mortality and 28-day mortality will be summarised by treatment group. The formal analysis will be undertaken for each the comparisons: AZD9773 dose 1 versus placebo, AZD9773 dose 2 versus placebo, AZD9773 dose 1 and 2 versus placebo separately using a Cochran-Mantel-Haenszel test in which the test will be stratified using the same covariates as for VFD. The corresponding relative risk, two-sided 80% CI and one-sided p-value will be calculated using the procedure PROC FREQ in SAS. Additionally, a two-sided 95% CI and two-sided p-value will also be presented.

An unstratified analysis will also be performed for the PP and ITT populations. Additionally, for the PP population, the impact of other baseline variables (examples include baseline TNF, Xigris use prior to study treatment and presence of shock at baseline) on the treatment comparisons will be explored by undertaking a series of analyses for each of the levels of these baseline variables separately, and the relative risks along with the associated two-sided 80% CIs from these analyses will be presented graphically.

In the event that the 7-day mortality and 28-day mortality status is unknown for some patients, they will be excluded from the PP population. However, for the ITT population they will be included as though they had died. Further sensitivity analyses may be undertaken depending on the number of such patients.

A Kaplan-Meier curve of time to death will also be produced and both a stratified (using the same covariates as for the analysis of 7 and 28-day mortality) and unstratified log rank test will be undertaken. If the 7-day or 28-day mortality status is unknown for some patients, they will be censored at the last known date the patient was alive.

Mortality at Day 90 will be considered in the same way as 7-day and 28-day mortality.

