7.6.10 Shock-free days

The number of shock-free days will be recorded up to Day 15. Shock-free is defined as a score <2 taken from the cardiovascular component of the modified SOFA score (see Appendix G).

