13.3 Methods of statistical analyses

13.3.1 Demographics, baseline characteristics, and concomitant medications

Demographic data, medical history, surgical history, Charlson Comorbidity Scale, physical examination (including dermal examination and lung auscultation), and key concomitant medications will be summarised. Concomitant medications will be coded using the AstraZeneca Drug Dictionary.

Patients who have to discontinue study treatment due to the administration of immunosuppressant medications, corticosteroids other than for adrenal replacement therapy, and anti-TNF antibodies during Days 1 to 6 will be summarised by treatment group.

Baseline disease characteristics including APACHE II Score, Glasgow Coma Score, TNF α , time of initial antibiotic dose relative to the qualifying organ failure and the number of patients with shock, on a ventilator, on vasopressors, with a positive culture or with renal impairment will also be summarised.

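### The shock-free days model has no baseline shock term and the organ failure-free days model only a partial baseline: a modest loss of precision, with no bias

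*Protocol*

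**What the plan says.** Section 13.3.6 of the protocol says: "Organ failure-free days, shock-free days, and ICU-free days will be summarised and analysed in the same way as for VFD". Section 13.3.4 sets out the VFD model as an analysis of covariance on treatment, APACHE II quartile, age group, region and "an indicator variable if the patient was on mechanical ventilation at baseline (two categories: yes or no"). The synopsis prescribes this covariate list for every formally analysed endpoint except mortality, so the list is fixed in the protocol itself.

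Both endpoints are built from the modified SOFA score. Section 7.6.10: "Shock-free is defined as a score <2 taken from the cardiovascular component of the modified SOFA score". Section 12.2.7 counts a day as organ failure-free when the organ's score is at most 1. The score is recorded at screening (Table 1 and section 7.2). Section 13.3.1 already plans to tabulate "the number of patients with shock, on a ventilator, on vasopressors" among the baseline characteristics.

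Inclusion criterion 4 admits patients with cardiovascular failure, respiratory failure or both. Section 6.2.1 adds: "Randomisation will not be stratified". Shock at baseline appears elsewhere only as an example variable for exploratory analyses run separately within each of its levels, in the PP population.

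**The concern.** The VFD model adjusts for whether the patient starts on a ventilator, which is the baseline state of that outcome. The same logic for shock-free days calls for a baseline shock term, and for organ failure-free days a baseline SOFA term. Copying the list unchanged leaves the first out and supplies the second only in part.

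At stake is the precision of two formally tested secondary endpoints, and their exposure to chance imbalance in a measured baseline factor. Section 13.1 warns that secondary endpoints may have to be read from their confidence intervals, so narrower intervals have practical value here.

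**Working it through.** **1. The plan's own figure.** Section 13.4 states that "100 patients per group will provide 90% power to detect an underlying true difference in means" between a dose and "placebo of 4.2 days using a 10% one-sided significance level", with SD 11.380.
- SE = 11.380 × √(2/100) = 1.609.
- Power = Φ(4.2/1.609 − 1.2816) = Φ(1.328) = 0.908.
- The required number is 97 per arm.

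The stated 90% with 100 per arm reproduces. It concerns VFDs only. The protocol gives no SD, effect or baseline correlation for shock-free or organ failure-free days, so everything below rests on assumed inputs.

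**2. Gain from a baseline shock term, shock-free days.** A covariate with correlation rho multiplies the residual SD by √(1 − rho²). If a one-sided 10% test has power B without the term, then with it:

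Power = Φ((1.2816 + z_B)/√(1 − rho²) − 1.2816)

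An illustrative simulation with assumed inputs (50% to 85% in shock at entry; mean shock duration 4.5 days where present) gave rho of 0.25 to 0.47.

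| rho | rho² | SE ratio | from 80% | from 90% |
|---|---|---|---|---|
| 0.25 | 0.06 | 0.968 | 81.9% | 91.4% |
| 0.47 | 0.22 | 0.883 | 87.0% | 94.8% |

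The gain is about 2 to 7 points from 80% and about 1 to 5 points from 90%. The 80% and 90% starting points are hypothetical.

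**3. Overlap with the existing covariates.** Only the variance explained beyond the four listed covariates counts. If that is 0.05, a test with 90% power reaches 91.1%, equivalent to 100/0.95 = 105 patients per arm without the term. If it is 0.10, the figures are 92.2% and 100/0.90 = 111.

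For ventilation, the entry rule helps. Table 2 requires mechanical ventilation for pulmonary qualification, so a non-ventilated patient must have qualified through vasopressor-dependent hypotension. Let v be the share ventilated and s the share of those in shock, and take all non-ventilated patients as in shock. Overall prevalence is p = vs + (1 − v), and the share of variance in shock explained by ventilation is [v(s − p)² + (1 − v)(1 − p)²]/[p(1 − p)].
- v = 0.6, s = 0.5: p = 0.70, and 0.06/0.21 = 29%.
- v = 0.9, s = 0.85: p = 0.865, and 0.002025/0.116775 = 2%.

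Over the assumed range (v 60% to 90%, s 50% to 85%), ventilation carries 2% to 29% of the information on shock, in the inverse direction. The overlap with APACHE II cannot be computed from the protocol.

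**4. Chance imbalance.** With 100 per arm and shock prevalence p, the between-arm difference has SD √(2p(1 − p)/100).

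| assumed p | SD (points) | chance of 10 points or more |
|---|---|---|
| 50% | 7.1 | 16% |
| 70% | 6.5 | 12% |
| 80% | 5.7 | 8% |
| 90% | 4.2 | 2% |

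If patients with and without baseline shock differ by 2 to 6 shock-free days (assumed), a 10-point imbalance moves the estimate by 0.2 to 0.6 days, before any part that the other covariates absorb.

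**5. Organ failure-free days.** Every patient enters with at least one qualifying organ failure, so the contrast between starting with and without shock does not carry over directly. Respiration is one of the five modified SOFA components (section 12.2.5), and its two highest scores require respiratory support (Appendix G). The ventilation indicator is therefore a partial own-baseline term. No calculation was made for this endpoint.

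**The case against.** The best defence is that nothing here is an error. Under randomisation, covariance analysis with any prespecified baseline set is valid, and one common set guards against picking covariates endpoint by endpoint. The endpoints are secondary, the trial is exploratory, and it was sized on 28-day VFDs alone. APACHE II already contains mean arterial pressure, oxygenation and creatinine. Baseline shock is examined within levels in the PP set, which is the lead efficacy population, and any imbalance would show in the baseline table.

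Much of this stands, and it limits the point to precision. Two parts carry less weight. APACHE II has no vasopressor item, whereas cardiovascular SOFA scores of 2 and above are defined by these drugs. The within-level analyses yield no overall shock-adjusted estimate in either PP or ITT.

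A reader might infer more than the documents support:
- That baseline shock is the dominant predictor of shock-free days. No passage says so, and the assumed rho of 0.25 to 0.47 corresponds to only 6% to 22% of variance.
- That power would rise by 8 points. That needs rho of 0.5 and a starting power of 80%, and this rho lies above the assumed range.
- That ventilation is an irrelevant covariate for both endpoints. It is part of the baseline for organ failure-free days and a weak, inverse marker of shock.
- That the comparison is biased or the error rate inflated. Neither follows.

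**Conclusion.** The point holds as a modest, optional improvement. The protocol fixes a covariate list that contains the outcome's own baseline for VFDs, none for shock-free days and a partial one for organ failure-free days, although the missing information is collected at screening. The cost is some lost precision and uncontrolled chance imbalance in shock. For shock-free days the sizes in steps 2 and 4 are upper figures, because overlap with APACHE II and ventilation has still to be taken off. They rest wholly on assumed correlations, prevalences and starting power. For organ failure-free days the case rests on the same principle, without a figure. The primary VFD analysis and its sample size are unaffected.

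**What to change.** In section 13.3.6 and the synopsis, keep the four covariates and add, for both the PP and ITT analyses:
- shock-free days: shock at baseline (cardiovascular modified SOFA of 2 or more, yes/no);
- organ failure-free days: baseline total modified SOFA, as a continuous term.

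The planned analysis of variance without covariates stays as the check.

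State a rule for missing baseline SOFA components, for example a missing-indicator category or a simple baseline imputation. The total needs five components, a carried-forward value may not exist at screening, and section 13.1 rules out imputation unless it is specified. Without a rule, ITT patients could drop out of the model.

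The cost is one degree of freedom per model, covariate sets that differ between endpoints, and the missing-baseline rule. No new data are needed.
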